1.5.1. Hepatic Injury

A number of on-going or completed clinical trials with AAV-based vectors have demonstrated the relative safety of this approach to treat various diseases such as hemophilia, spinal muscular atrophy (SMA) and other genetic disorders. The most consistent treatment-emergent adverse reaction has been elevations in liver enzymes, mostly related to high (>1E+12 vg/kg) vector doses. The timing of the asymptomatic liver enzyme elevations post-gene transfer has varied, but most have been adequately treated with the addition of corticosteroids with no impact on transgene expression. Additionally, subjects treated with AAV-based vectors typically generate an immune response to the AAV capsid and may develop a cellular response to the transgene. In an attempt to reduce any inflammatory and immune responses to the vector, subjects in an ongoing trial are now receiving steroids for several weeks after vector delivery.

To address the shortcoming of the standard paradigm for monitoring of liver health in DMD patients, glutamate dehydrogenase (GLDH) has been identified as a liver-specific biomarker of liver injury that is independent of muscle damage.⁵⁰ In these studies, GLDH has been found to be as effective as ALT in diagnosing liver injury. Thus, GLDH will be used as a sensitive biomarker of liver injury in this study and may be used to guide additional

immunomodulatory intervention, as well as to confirm potential cases meeting Hy's law criteria based on elevations of bilirubin alone (in the context of elevated AST/ALT due to muscle damage).

As with other gene therapy clinical studies, elevations in liver enzymes are not unexpected. In this study, all subjects will have received glucocorticoids for at least 6 months, with a stable daily regimen for at least 3 months prior to the Baseline visit, and will continue to receive elevated daily doses of glucocorticoids for at least 3 months post-infusion of investigational product before returning to their pre-study doses of glucocorticoids for at least the remainder of the first year post-infusion. It is anticipated that the pre-existing steroid regimen along with the 3-month modified regimen may assist in controlling potential AAV-mediated liver injury. However, should liver injury be detected, the glucocorticoid doses may need to be increased further, or other immunomodulatory therapy initiated, in consultation with the assigned immunopharmacologic and/or hepatic experts.

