Although it has not been described, either in previous dystrophin gene therapy clinical trials, or in pre-clinical models, a cellular immune response to newly and widely expressed dystrophin could theoretically induce local tissue damage related to the site of new protein expression, which would have the potential for clinical manifestation as a myositis or myocarditis. Both will be difficult to monitor in the setting of DMD, given the degree of ongoing muscle and myocardial damage related to the disease but will require a low threshold for diagnostic consideration.

A diagnosis of myositis might be considered in the event of evidence of increasing muscle pain or weakness associated with a rising creatine kinase (CK) or C-reactive protein (CRP). MRI and comparison to baseline scans may aid in the diagnosis. Myocarditis may be considered in the event of increased or new cardiac symptoms, an increased cardiac troponin I (cTnI) and creatine kinase myocardial b fraction (CK-MB), CRP, or as evidenced on electrocardiogram (ECG) or cardiac MRI (or echocardiogram).

Furthermore, the study will utilize an external data monitoring committee (E-DMC) to provide an objective assessment of safety, and which may include an expert in clinical immunopharmacology (eg, clinical immunologist, rheumatologist, transplant physician) for *ad hoc* consultation should the need arise (Section 9.6).

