 - Preexisting values of TBili above the normal range: TBili level increased from baseline value by an amount of at least 1 × ULN **or** if the value reaches >3 × ULN (whichever is smaller).

Rises in AST/ALT and TBili separated by more than a few weeks should be assessed individually based on clinical judgment; any case where uncertainty remains as to whether it represents a potential Hy's law case should be reviewed with the sponsor.

In addition, however, as described in Section 1.5.1, in DMD patients, the standard biomarkers of the onset of hepatocellular injury such as ALT and AST are not capable of detection of liver damage due to the release of these enzymes from diseased skeletal muscle. To address the shortcoming, elevations of GLDH >2 x ULN will also be assessed individually based on clinical judgment and with the support of the *ad hoc* hepatic and/or immunopharmacologic expert (s) supporting the E-DMC; any case where uncertainty remains as to whether it represents a potential Hy's law case should be reviewed with the sponsor. Subjects who experience a consistent GLDH elevation above 3 × ULN may also be monitored more frequently to determine if they are an "adaptor" or are "susceptible", as defined above.

If any of the above criteria is met, the subject should return to the investigator site and be evaluated as soon as possible, preferably within 48 hours from awareness of the abnormal results. This evaluation should include laboratory tests, detailed history, and physical assessment.

In addition to repeating measurements of AST and ALT and TBili, laboratory tests should include albumin, creatine kinase (CK), direct and indirect bilirubin, gamma-glutamyl transferase (GGT), GLDH, prothrombin time (PT)/international normalized ratio (INR), total bile acids, alkaline phosphatase and acetaminophen drug and/or protein adduct levels.

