3. ENDPOINTS AND BASELINE VARIABLES: DEFINITIONS

3.1. Primary Endpoints

- Incidence of both dose-limiting and treatment-related AEs, inclusive of infusion and injection site reactions, through 1 year post-treatment.
- *Incidence, severity, and causal relationship of TEAEs through 1 year posttreatment.*
- Incidence and magnitude of abnormal laboratory findings through 1 year posttreatment.
- Abnormal and clinically relevant changes in physical and neurological examinations, weight, vital signs, ECG, cardiac MRI (or echocardiogram-) measured LVEF, CSSRS through 1 year posttreatment.

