6.1.2. Laboratory Data

Central and local laboratory results will be combined for reporting purposes. Baseline is as defined in Section 3.1.2. Laboratory data including hematology, chemistry and urinalysis will be listed. If there is a local and central laboratory collection on the same day, the central laboratory value will be used for analysis.

The following will be summarized by dose cohort and ambulatory status at baseline. To evaluate the safety of sirolimus, the incidence and magnitude of abnormal laboratory findings through 30 days post the last dose of sirolimus administration will be summarized by sirolimus cohort (sirolimus, non-sirolimus) if there are at least 3 participants in each cohort. No summaries will be provided by sirolimus cohort status since only one participant received sirolimus.

• Incidence of laboratory test abnormalities without regard to baseline abnormality, for normal baseline, and for abnormal baseline.

For select laboratory parameters, data will be summarized by visit descriptively in tabular format and displayed graphically as described below.

Parameter	Presentation			
	Table: Shift table: Graph, Box-plo			
	Changes and Percent	<lln*,< td="">Changes from	</lln*,<>	Changes from	
	changes from baseline	Normal*,	baseline	
	By visit	>ULN	By visit	
		By visit		
GLDH	X	X	X	
CK	X	X	X	
C3 and C4	X		X	
Platelets	X		X	
Creatinine	X		X	

^{*}If the normal range is \leq or \leq ULN without the LLN, then the category \leq LLN will not be presented.

The shift tables will use baseline values categorized as < LLN, Normal, and > ULN, with the shifts being shown into the same categories.

For laboratory parameters summarized descriptively, if the raw laboratory values are obtained using different normal ranges over time or across participants, external normalized values that are normalized to pediatric textbook ranges will be used to summarize the results.

To assess the effect of sirolimus on complement activation, the C4 levels and platelet levels will be summarized descriptively and/or graphically by sirolimus cohort if there are at least 3 participants in each cohort as follows:

- Percent change from baseline to nadir through Day 30 post-fordadistrogene movaparvovec infusion

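### The GLDH shift table has a single category above ULN, so it cannot count participants who cross the protocol's own 2x and 3x ULN levels

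*SAP*

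**What the plan says.** SAP Section 6.1.2 has a table of selected laboratory parameters. GLDH and CK are the only two in it with a shift table, and both also get by-visit change, percent-change and box-plot displays. The shift categories are fixed in one sentence: "The shift tables will use baseline values categorized as < LLN, Normal, and > ULN, with the shifts being shown into the same categories".

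The protocol gives GLDH a special role. Section 1.5.1 states that "GLDH will be used as a sensitive biomarker of liver injury in this study". Section 8.4.2 gives the reason: in DMD, ALT and AST "are not capable of detection of liver damage due to the release of these enzymes from diseased skeletal muscle". The same section sets two GLDH levels. First, "elevations of GLDH >2 x ULN will also be assessed individually based on clinical judgment". Second, "Subjects who experience a consistent GLDH elevation above 3 × ULN may also be monitored more frequently". Exclusion criterion 9 in Section 4.2 removes subjects only when screening GLDH is above 2x ULN.

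The primary laboratory endpoint (SAP Section 3.1) is "Incidence and magnitude of abnormal laboratory findings through 1 year posttreatment", so it covers size as well as occurrence.

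For CK the protocol sets no multiple of ULN. Section 1.5.2 treats a rising CK or CRP, together with worsening muscle pain or weakness, as a reason to consider myositis.

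**The concern.** A shift table is where a reader looks for how many participants moved from one clinically meaningful band to another. With one open-ended band above ULN, the GLDH table does not use the levels at which the protocol looks at a case. It fails in two ways:

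- A participant who starts normal lands in the same cell whether the later value is barely above ULN or many times above it.
- A participant who starts above ULN cannot move upward at all, however large the rise.

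Elevations are not hypothetical. The rationale for Amendment 7 in Protocol Appendix 3 records that the E-DMC had already reviewed three cases of elevated GLDH. What is at stake is whether the study report states how many participants reached the protocol's own levels, by dose cohort and ambulatory status, or leaves the reader to work it out.

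**Working it through.** The SAP gives no figure to reproduce. The check is on the logic of the categories.

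**Inputs.** Shift categories <LLN, Normal, >ULN (SAP 6.1.2). GLDH levels >2x and consistently >3x ULN (Protocol 8.4.2). Screening limit >2x ULN (Protocol 4.2). Group sizes 3, 16 and 3 (SAP 2.5). The baseline and post-baseline values below are illustrative.

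**Step 1: cells.** Let b and p be the baseline and post-baseline values in multiples of ULN. A value is >ULN if it exceeds 1, otherwise Normal (LLN does not matter for rises). Percent change = 100 x (p/b - 1).

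| b | p | % change | Cell in the SAP table | Cell if split at 2x and 3x |
|---|---|---|---|---|
| 0.8 | 1.1 | +37.5 | Normal to >ULN | <=ULN to >1-2x |
| 0.8 | 2.1 | +162.5 | Normal to >ULN | <=ULN to >2-3x |
| 0.8 | 8.0 | +900 | Normal to >ULN | <=ULN to >3x |
| 1.5 | 1.9 | +27 | >ULN to >ULN | >1-2x to >1-2x |
| 1.5 | 2.1 | +40 | >ULN to >ULN | >1-2x to >2-3x |
| 1.5 | 3.1 | +107 | >ULN to >ULN | >1-2x to >3x |
| 1.5 | 8.0 | +433 | >ULN to >ULN | >1-2x to >3x |

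The SAP table has two distinct results for these seven cases. The split table has six.

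**Step 2: can percent change stand in?** The change needed to pass level t is 100 x (t/b - 1). For t = 3 it is +200% from b = 1.0, +100% from b = 1.5 and +50% from b = 2.0. In reverse, a doubling gives 1.6x ULN from 0.8 and 4.0x from 2.0. Percent change therefore does not identify who crossed 2x or 3x ULN.

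**Step 3: group summaries.** One participant at +100%, with the others unchanged, moves the mean percent change by 100/3 = 33.3 points in a group of 3 and by 100/16 = 6.25 points in the group of 16. The rise still shows in the group maximum, which SAP 5.2.1 requires.

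**Step 4: other planned outputs.**

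- *Incidence of abnormalities, split by baseline status (SAP 6.1.2).* No multiples of ULN are stated. SAP 3.1.2 ties abnormality criteria to hematology, chemistry and urinalysis and mentions GLDH separately. Protocol Table 1 lists GLDH under Other. Its inclusion is neither confirmed nor excluded.
- *eDISH plot (SAP 6.1.2).* It plots AST or ALT against bilirubin. The attached listing of GLDH over time covers only the upper-right quadrant, so an isolated GLDH rise does not reach it.
- *By-visit summaries.* SAP 5.3.6 takes the value nearest the target day unless specified otherwise. Appendix 2, with the windows, is not in the public text, so whether an off-schedule peak enters is unknown.
- *cTn-I (SAP 6.1.2).* Here the SAP counts values >3x baseline in participants who start above ULN and >3x ULN in the others, over planned and unplanned visits. GLDH and CK get no equivalent.

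**Step 5: CK.** The share f of participants above ULN at baseline is not in the documents, so it is an assumption, shown over its range. If CK doubled in all 16 ambulatory high-dose participants, the number whose rise could not register because they started above ULN is 16f: 0 at f = 0, 8 at f = 0.5, 16 at f = 1.

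**The case against.** A reader might infer that liver or muscle signals vanish from the analysis. The documents do not support that. Change and percent-change tables carry minima and maxima, box-plots show the distribution of change, and SAP 6.1 has the safety endpoints listed as well as summarized. With 22 participants, a listing is a workable way to find who crossed a level. A GLDH elevation that leads to further diagnostic work-up would also be recorded as an adverse event under Protocol 8.2.2 and tabulated. All of this stands. The gap is a missing count in the summaries, not missing data.

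A reader might also treat the GLDH levels as stopping rules. They are not. Above 2x ULN prompts case-by-case judgment. The 3x prompt needs a consistent elevation and only permits closer monitoring. Enrollment halts in Protocol 3.5 name Hy's Law, alkaline phosphatase and bilirubin. The Amendment 7 rationale adds that the E-DMC saw no need to review later GLDH cases unless Hy's Law was met. That lowers the urgency. It also means a table of worst values above 3x would not by itself reproduce the 3x prompt, because it counts single transient values.

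Finally, it is tempting to say the CK table holds no information on increases because every boy with DMD starts above ULN. Neither document says so. The enzyme-release sentence in Protocol 8.4.2 concerns ALT and AST. Nor does the protocol give a CK cut-off, and rising CK is visible in the planned change displays.

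**Conclusion.** The point holds for GLDH as a reporting gap of modest weight. By construction, the shift table cannot show how many participants exceeded 2x ULN or were consistently above 3x ULN, and it scores every further rise from an above-ULN baseline as no shift. No other stated output supplies the count. This follows from the category definitions and needs no distributional assumption. How many participants are affected cannot be stated: the documents do not say how many, if any, started between 1x and 2x ULN.

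For CK the same limit applies to each participant above ULN at baseline and to nobody else. Its reach depends on the assumed share f.

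No hypothesis test or decision rule uses these tables, so no conclusion of the trial turns on them. The case for change is that the primary endpoint asks for magnitude, GLDH is the marker the protocol relies on, and the SAP already uses multiples of baseline and of ULN for cTn-I.

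**What to change.** In SAP Section 6.1.2:

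1. Replace the GLDH categories with <=ULN, >1 to 2x, >2 to 3x and >3x ULN. Tabulate baseline by worst post-baseline value, using planned and unplanned visits, by dose cohort and ambulatory status as already planned.
2. Report separately the number of participants with GLDH above 3x ULN on repeated measurements, and state what counts as repeated, since the protocol's consistent elevation is not defined further.
3. For participants with CK above ULN at baseline, add a fold-of-baseline summary on the cTn-I pattern, with the limits chosen by the sponsor.

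The cost is table-shell wording and a few more rows. No new data are needed and clinical management is unchanged. The downside is sparseness: the two groups of 3 participants will leave most cells empty, and there the listing remains the more useful display.

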3.3. Duration of Subject Participation

Willing and eligible subjects will participate in the trial for approximately 5.5 years, and visits will include the following:

- Screening: approximately 2 days of assessments across 2-3 visits within an approximately 26-week period relative to the Baseline visit;
- Baseline: approximately 2 days of assessments across 1-2 visits within a 2-week period;
- Treatment: approximately 2 visits: 1) single administration of PF-06939926 followed by at least 24 hours of in-patient monitoring (ie Days 1 and 2), and 2) 2-week follow-up in which subjects will remain local to the investigational site, and complete 1-day visits occurring on Days 4, 7, and 10 (±1 day) for blood sample collection and safety monitoring, as well as sample collection for local laboratory testing on Days 5-9, or longer, as clinically indicated;
- 1st Year Follow-up: approximately 1 to 3 days of assessments for 6 visits, as well as 8 remote visits (eg, blood sample collection at subject's home, virtual wellness check-ins that include AE assessments, activity monitoring), during the first 12 months following the single administration of PF-06939926;
- Long-Term Follow-up: total of 4 annual, 2 or 3-day visits starting approximately 2 years following the single administration of PF-06939936, as well as 4 remote visits (eg, blood sample collection in the subject's home, virtual wellness check-ins) in between the 4 annual visits.

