2.5. Study Design

This FIH/FIP study is an open-label, multi-center, ascending dose study designed to evaluate the safety and tolerability of a single IV infusion of fordadistrogene movaparvovec in

participants with DMD. There are 22 participants who received a single dose of fordadistrogene movaparvovec between 1E14 vg/kg and 3E14 vg/kg per the ITR-based method or 2E14 vg/kg per the TG-titer method.

Fordadistrogene movaparvovec at 3E14 vg/kg per the ITR-based titer method is approximately equivalent to 2E14 vg/kg per the TG-titer method. Therefore, participants dosed at 3E14 vg/kg per the ITR-based titer method or at 2E14 vg/kg per the TG-titer method will be grouped in the high dose cohort.

- 1. Ambulatory low dose cohort (N=3): 1E14 vg/kg based on the ITR method
- 2. Ambulatory high dose cohort (N=16): 3E14 vg/kg based on the ITR method or 2E14 vg/kg based on the TG method
- 3. Non-ambulatory high dose cohort (N=3): 2E14 vg/kg based on the TG method
 - Sirolimus non-ambulatory high dose cohort (N=1): 2E14 vg/kg per the TG-based titer method.

Note that a safety profile will be provided for the one participant who received sirolimus. No other summaries will be provided since only one participant received sirolimus.

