6. ANALYSES AND SUMMARIES

6.1. Primary Endpoints

The safety and other endpoints detailed in Section 3.1 will be listed and summarized, where the resulting data presentations will consist of participants from the Safety Analysis Set (as defined in Section 4).

Primary safety analyses will be based on the data through 1-year post-treatment of fordadistrogene movaparvovec. Secondary safety analyses will be based on the long-term follow up data through 5-years post-treatment of fordadistrogene movaparvovec. Adverse events, ECGs, vital signs, physical and neurological examinations, cardiac MRI (or echocardiogram) and safety laboratory data will be reviewed and summarized on an ongoing basis during the study to evaluate the safety of participants. Safety data will be presented in tabular and/or graphical format and summarized descriptively, where appropriate. Analysis windows for these summaries and graphical displays by visit are provided in Appendix 2.

All analyses will be conducted by dose cohort and ambulatory status at baseline to evaluate the safety and tolerability of administering fordadistrogene movaparvovec.

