- Summary statistics including the mean, the location, the location shift between the sirolimus cohort and non-sirolimus cohort, and the corresponding 95% CI (when n ≥ 3) over time and at nadir based on the Hodges-Lehmann method (Hodges & Lehmann, 1963⁵; Hodges Jr & Lehmann 1983⁶).

The nadir is defined as the lowest measurement observed between baseline through Day 30 visit post-fordadistrogene movaparvovec infusion.

No summaries will be provided by sirolimus cohort status since only one participant received sirolimus.

cTn-I:

Baseline values will be categorized as Normal (within Normal Range) and above ULN. The shifts in categories over time showing the number and percent of participants in each category will be presented.

The participants will be divided into two categories: those with baseline cTn-I \leq 99th percentile (ie, ULN) and those with baseline cTn-I > 99th percentile (ie, ULN). For Centaur assay, the cTn-I 99th percentile (ie, ULN) will be 0.03 ng/mL. The LLOQ is 0.03 and values below LLOQ will set to 0.029. For the Beckman assay, the cTn-I 99th percentile (ie, ULN) will be 19.8 ng/L. The LLOQ is 2.3 ng/L and values below LLOQ will be set to 2.29 ng/L.

For participants with baseline cTn-I > 99th percentile (ie, ULN):

- a. Count the number of post-baseline visits at which cTn-I was >3X baseline for each participant. Present the number and percentage of participants who had 0, 1, 2, or 3 visits at which cTn-I was >3X baseline.
- b. For post-baseline visits with cTn-I > 3X baseline, present descriptive summary statistics (mean, SD, median, Q1, Q3, minimum and maximum) for the maximum cTn-I level.

Graphical displays:

• Spaghetti plot including participants with ≥ 2 visit assessments post-baseline that are >3X baseline.

For participants with baseline cTn-I ≤ 99th percentile (ie, ULN),

- a. Count the number of post-baseline visits at which cTn-I was >3X 99th percentile (ie, ULN) for each participant. Present the number and percentage of participants who had 0, 1, 2, or 3 visits at which cTn-I was >3X 99th percentile (ie, ULN).
- b. For post-baseline visits with cTn-I >3X 99th percentile, present descriptive summary statistics (mean, SD, median, Q1, Q3, minimum and maximum) for the maximum cTn-I level.

Graphical displays:

• Spaghetti plot including participants with ≥ 2 visit assessments post-baseline that are $> 99^{th}$ percentile (ie, ULN).

All visits (ie, planned and unplanned) will be included in these analyses.

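### The cTn-I frequency table stops at 3 elevated visits, although Year 1 alone has 14 planned follow-up visits, so a participant with 4 or more has no row

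*SAP*

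**What the plan says.** SAP section 6.1.2 splits participants by baseline cTn-I, above the ULN or at or below it. Within each stratum it counts, per participant, the post-baseline visits at which cTn-I is more than three times a reference value.

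- Baseline above ULN (reference: own baseline): "Present the number and percentage of participants who had 0, 1, 2, or 3 visits at which cTn-I was >3X baseline".
- Baseline at or below ULN (reference: ULN): "Present the number and percentage of participants who had 0, 1, 2, or 3 visits at which cTn-I was >3X 99th percentile (ie, ULN".

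The section adds: "All visits (ie, planned and unplanned) will be included in these analyses". No upper limit is placed on the count, and neither list contains an open-ended category.

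Three other cTn-I outputs are planned in the same section: a shift table between normal and above ULN, a summary of the maximum level at visits that exceed the threshold, and spaghetti plots. The plot for the stratum with raised baseline has an open-ended entry rule: "Spaghetti plot including participants with ≥ 2 visit assessments post-baseline that are >3X baseline".

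On the number of visits, Protocol section 3.3 describes first-year follow-up as "approximately 1 to 3 days of assessments for 6 visits, as well as 8 remote visits" and long-term follow-up as a "total of 4 annual, 2 or 3-day visits starting approximately 2 years following the single administration", with 4 remote visits in between. SAP section 6.1 says: "Secondary safety analyses will be based on the long-term follow up data through 5-years post-treatment of fordadistrogene movaparvovec".

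**The concern.** The rule counts without a cap but reports into a closed list. A participant with 4 or more elevated visits is counted and then has nowhere to go. Followed literally, the table omits him and its percentages no longer sum to 100% of the stratum.

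The omission is selective, because those without a row are by construction the participants with the most repeats. This is also the section's only tabulation of how often an elevation recurs. The shift table uses only two categories, and the maximum-level summary describes height, not repetition.

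The parameter matters here. Abnormal laboratory findings through 1 year are a primary endpoint (Protocol section 2). Protocol section 1.5.2 names raised cTnI among the findings that may point to myocarditis, and section 3.5 makes a clinical diagnosis of myocarditis a reason to halt enrollment pending E-DMC review. With 22 participants, one missing person visibly changes a table.

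**Working it through.** **Is cTn-I measured at every follow-up visit?** Protocol Table 1 lists it in the chemistry panel. Magnesium and CK-MB carry timing footnotes there; cTn-I carries none. The clinical safety row of the Schedule of Activities, which refers to Table 1, is marked in every first-year follow-up column.

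**Planned Year 1 visits.** Reproducing the figure in Protocol section 3.3 from the Schedule of Activities:

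- In-person: Visits 4, 6, 8, 10, 12, 13 = 6
- Remote: Visits 5, 7, 9, 11.1, 11.2, 11.3, 12.1, 12.2 = 8
- Total: 6 + 8 = 14, which agrees

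Visit 3 also has post-dose draws on Days 2, 4, 7 and 10. Counted as one visit it gives 14 + 1 = 15; with the draws counted separately, 14 + 4 = 18.

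**Through Year 5.** SAP section 6.2.3 repeats the section 6.1 safety analyses on all data to 5 years. Years 2 to 5 add 4 annual and 4 remote visits, so 14 + 8 = 22 (23 with Visit 3 as one visit; 26 with its draws separate). Unplanned visits come on top. Protocol section 7.2.12 asks for a repeat cTnI within 24 to 48 hours of a triggering value, so extra measurements fall on participants who already have high values.

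**When a count of 4 first becomes possible on planned visits.** Leaving out Visit 3, the first four are Visits 4, 5, 6 and 7, so Day 45. With Visit 3 as one visit they are Visits 3, 4, 5 and 6, so Day 30.

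**Counts without a row.** With 14 visits the count can be 0 to 14, which is 15 values. Rows exist for 4 of them, so 15 − 4 = 11 (counts 4 to 14) have none.

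**Effect of one omitted participant on the row total.** SAP section 2.5 gives cohorts of 3, 16 and 3. If a whole cohort fell in one baseline stratum, the four percentages would sum to:

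- Cohort of 16: 15/16 = 93.8%
- Cohort of 3: 2/3 = 66.7%

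These are upper bounds. Splitting a cohort by baseline cTn-I makes the denominator smaller and the shortfall larger.

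**How likely is a count of 4 or more?** The documents give no rate. Purely as an illustration, assume independent visits with the same probability of an elevated value at each of 14 visits. The chance that a participant reaches 4 or more is then:

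| Assumed probability per visit | Chance of 4 or more |
|---|---|
| 0.05 | 0.4% |
| 0.10 | 4.4% |
| 0.20 | 30.2% |
| 0.30 | 64.5% |

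Repeated values in one participant are unlikely to be independent, so this shows only that the answer depends on an unknown rate. The conclusion does not rest on it.

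**The case against.** The strongest reply is that nothing is truly lost. Given the stratum size, the number with 4 or more visits equals that size minus the sum of the four rows. Such participants also enter the maximum-level summary and meet the entry rule of two or more visits for the spaghetti plot, and their values are in the laboratory listings. With 22 participants a reader can follow each one.

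Most of this stands, and it is why the harm is limited. It does not make the table right. A reader who sees percentages short of 100% must infer the reason, and a shortfall could equally be taken for missing data. In the stratum with normal baseline, the plot selects on values above the ULN, not above three times the ULN, so it does not isolate the group missing from the table.

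A second reply is that the list may be shorthand, or may reflect counts already seen. The cTn-I analyses were added in SAP version 6, after version 5 had recorded that enrollment was over, and the study is open-label. The documents do not settle this. The text does not say that 3 means 3 or more, and the same section writes an open-ended count where it wants one.

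Third, the analysis windows are in SAP Appendix 2, which is not in the public text. The totals above are therefore counts of protocol visits, not confirmed counts of cTn-I analysis visits. That weakens the exact ratios. It does not remove the possibility of counts above 3, since the SAP includes all planned and unplanned visits.

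**Conclusion.** The point holds. In both baseline strata the categories are not exhaustive for the count they are meant to report. On planned visits alone the count can reach 14 in Year 1 (15 with Visit 3 as one visit) and 22 (23) through Year 5, against a highest row of 3. One affected participant would bring the row total down to at most 93.8% in the cohort of 16 or 66.7% in a cohort of 3.

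This rests on two readings: that cTn-I is drawn wherever the Table 1 safety panel is scheduled, and that the last row means exactly 3, as written. The size is conditional. Nobody may reach 4 visits, in which case the table is complete as it stands. Incidence of any elevation above three times the reference is recoverable from row 0 in every case. No test, threshold or analysis population is affected. It is a fault in a descriptive safety table that should be corrected, not one that threatens the study's conclusions.

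**What to change.** In SAP section 6.1.2, for both baseline strata, either keep rows 0, 1, 2 and 3 and add a row for 4 or more visits, or make the last row 3 or more visits. The first option keeps more detail. A column giving the number of evaluable cTn-I visits per participant would help in reading the counts but is optional.

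The cost is one added or relabelled row in two table shells and a few words in the SAP. It needs no new data and changes no threshold or population.
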